3. STUDY PROCEDURES

- Patients who are seen in clinic for rotator cuff pathology will undergo treatment for their rotator cuff based

on a shared decision-making process with the orthopedic surgeon, irrespective of this study. Once a treatment plan is in place, the patient will be introduced to this study and presented with the opportunity to participate. If the patient agrees, a formal consent process will take place in clinic and the patient will undergo initial, baseline testing of strength, range of motion, pain scores, and patient reported outcome scores.

Therefore, patients will be either in the nonoperative arm or the operative arm of this study. Within each arm, patients will be randomized via computer to be placed in either the blood flow restriction (BFR) cohort or the traditional (non-BFR cohort). Patients will prospectively undergo rotator cuff rehabilitation using BFR or conventional therapy by physical therapists with extensive experience in rotator cuff rehabilitation who will undergo training on use of BFR.

The nonoperative group will be given identical rehabilitation protocols, with the only difference being the use of a BFR cuff during rehabilitation for the BFR cohort. Similarly, the operative group will be given identical rehabilitation protocols, with the only difference being the use of a BFR cuff during rehabilitation for the BFR cohort.

Patients undergoing operative rotator cuff repair (RCR) will undergo preoperative rehabilitation prior to surgery for two weeks. Due to limitations of health insurance coverage of physical therapy sessions, the two weeks of preoperative "prehab" will consist of a structured home exercise program that is taught to the patient by a physical therapist during one session and recorded on a physical therapy (PT) diary by the patient during the two weeks leading up to surgery. Patients will be provided with video instruction and training on how to conduct the exercises and this will also be done with and without the use of BFR depending on group allocation (via randomization). Additionally, warning signs for BFR cuff intolerance such as increased pain, swelling, numbness/tingling of the arm will be communicated to the patient. Following surgery patients will immediately be started in a formal physical therapy regimen as an outpatient. Therapy will consist of a structured program progressing from range of motion to strength training and then functional tests. Patients will remain in their allocated BFR or non-BFR group.

Protocol as follows, both groups will use the same protocol with the only difference being use of BFR:

For surgical patients:

- Preop: Patients will undergo a home program consisting of isometric exercises including shoulder extension, abduction, external rotation and internal rotation pushing against a wall.

For both surgical and non-surgical patients:

- Post-op weeks 0-8: Passive shoulder range of motion (ROM) only
- Sling immobilization with active elbow, wrist and hand ROM
- Passive ROM only of shoulder including pendulums, supine elevation in scapular plane, external rotation with arm at side.

8-12 weeks being more active range of motion

- Discontinue sling
- Being active exercises including prone row, standing internal/external rotation with bands, wall slides into shoulder flexion

Weeks 12-20: Strength and function of Side lying shoulder external rotation, increase resistance band exercises

Throughout this protocol patients will have a pre-operative visit, an early 2 week post operative visit to check range of motion and wound healing, a six week visit to monitor range of motion and potentially clear for active ROM and sling discontinuation, and a three month visit prior to clearance to being return to more aggressive activity. Strength and range of motion will be recorded at each of these visits in order to assess the primary endpoint.

Outcomes:

Primary Outcome:

- Strength to be measured via dynamometer at each clinic visit

Secondary Outcomes:

- Range of motion via goniometer
- Pain via visual analogue scale (VAS) pain scale at each visit
- Patient reported outcomes scores at each visit
- Fatty infiltration and muscle atrophy measured via ultrasound and compared to pre-operative imaging

Plan to recruit patients starting in June 2020. Will enroll patients and collect data from June-2020 to May 2021. Manuscript writing and submission to occur in June 2021.

Data analysis: The primary endpoint of this study was a maximum repetition total work deficit of 15% between the BFR and control group as measured by dynamometer. This was based on previous data showing that a strength deficit of 15% represents a clinically significant difference that is not likely attributable to limb dominance. Work deficit was calculated in each group by comparing the operative leg with the nonoperative leg to obtain a deficit percent. A power analysis was performed before the study to assess the number of patients needed to detect a 15% total work deficit between the BFR and control groups. With a power of 80% (beta level $\frac{1}{4} 0.80$, alpha level $\frac{1}{4} 0.05$), a sample size of 34 (17 patients per group) was obtained. Data will be provided to and analyzed by trained statisticians to determine differences in primary and secondary outcomes.

All continuous data will be analyzed using independent 2-group t tests and reported as means \pm standard deviations. Categorical data will be compared between the 2 groups using chi-square tests and reported as counts and percentages. A preliminary test to confirm the quality of variances will be conducted prior to utilizing the t test to confirm the appropriate statistical analysis. Nonparametric equivalents Wilcoxon rank-sum and Fisher exact tests will be used as needed for nonnormal distributions and low variable numbers, respectively. A multivariable regression analysis was performed to assess potential confounding demographic variables.

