1. STUDY AIM, BACKGROUND, AND DESIGN ABSTRACT

The purpose of this study is to examine the effect of utilizing blood flow restriction (BFR) therapy in patients treated both non operatively and operatively for rotator cuff tears (RCT). BFR has been proposed to work by restricting arterial inflow leading to an oxygen depleted environment and the ability to induce muscle adaptation at lower maximum repetition via reactive hyperemia. Muscle atrophy occurs following rotator cuff tear. Thus, physical therapy is used to regain strength with the ultimate goal of returning to activity.

The goal of this investigation is to determine if using BFR during therapy for non-operatively managed and operatively managed rotator cuff tears would lead to increased and expedited strength gains. Additionally, the investigators would like to determine if BFR is beneficial in preventing muscle atrophy and fatty infiltration often seen in the setting of rotator cuff tear, as it is known that cuff tears can subject the muscles to degenerative changes and these patients are at risk for poorer clinical outcomes. The investigators will also look at patient reported outcomes metrics and pain scores to determine if BFR has a significant impact on the patient experience surrounding rotator cuff tear after both nonoperative treatment with therapy and operative treatment with surgical repair and peri-operative rehabilitation.

The investigators hypothesize that the BFR group will have significantly greater strength gains at all time points. Previous studies have shown that BFR has potential in increasing muscle torque generation and cross-sectional area in the first six months following anterior cruciate ligament (ACL) reconstruction. While there have not been as many studies investigating the use of BFR following upper extremity surgery, previous research has demonstrate that BFR can be useful both proximal and distal to the targeted muscle groups in the upper extremity. In addition to the paucity of research on post-operative BFR following rotator cuff repair (RCR), there is no evidence on pre-operative use as well. The investigators believe that the use of BFR in the perioperative period surrounding rotator cuff tear and repair has the potential to significantly decrease muscle atrophy and lead to faster, more substantial strength gains and less muscle atrophy and fatty infiltration.

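### Strength is primary at every visit, but no primary visit, multiplicity rule or arm handling is named, although the stated power fits one test

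*Combined protocol and SAP*

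**What the plan says.** All references are to the combined protocol and SAP.

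- **Hypothesis (section 1):** "the BFR group will have significantly greater strength gains at all time points".
- **Primary outcome (section 3, outcomes):** "Strength to be measured via dynamometer at each clinic visit". The visits listed are one before surgery and three after it, at 2 weeks, 6 weeks and 3 months. On their use the text says: "Strength and range of motion will be recorded at each of these visits in order to assess the primary endpoint".
- **Endpoint and power (section 3, data analysis):** the endpoint is "a maximum repetition total work deficit of 15% between the BFR and control group as measured by dynamometer", a percentage deficit of one limb against the other. With 80% power and alpha 0.05, "a sample size of 34 (17 patients per group) was obtained". No SD, sidedness or visit is attached.
- **Method (section 3, data analysis):** "All continuous data will be analyzed using independent 2-group t tests". A multivariable regression for demographic confounders is also mentioned. There is no repeated-measures analysis and no multiplicity rule.
- **Randomisation (section 3):** "Within each arm, patients will be randomized via computer to be placed in either the blood flow restriction (BFR) cohort" or the conventional-therapy cohort. The arms are operative and nonoperative. The analysis text does not say whether they are pooled, or whether the 34 patients cover one arm or both.
- **Rehabilitation (section 3):** "Post-op weeks 0-8: Passive shoulder range of motion (ROM) only". Active exercise follows in weeks 8 to 12 and strengthening in weeks 12 to 20.

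**The concern.** The between-group contrast is stated: BFR versus control in percentage work deficit, by t test. What is missing is the visit at which it is made, whether it is a level or a gain (section 1 speaks of gains, section 3 of a deficit), and which patients it covers. As written, the plan yields at least three primary results and no rule for turning them into one conclusion.

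Under either natural rule the trial does not have the properties it states. Requiring success at every visit lowers power below 80%. Accepting success at any visit raises the false-positive rate above 5%. Nothing stops the choice from being made after the data are seen.

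A second problem concerns the week 2 reading. It falls in the passive-only phase, and the plan does not say what kind of strength test is done then.

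**Working it through.** **Inputs from section 3.** Three post-operative visits; 17 per group; 80% power; alpha 0.05; target difference 15 percentage points.

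**Assumptions, not in the documents.** Two-sided tests; equal correlation between visits, from 0 to 0.9; the same effect at each visit, so that each visit alone has 80% power.

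**1. The plan's own figure.** Without an SD, 34 can only be back-solved. For a two-sample t test with 17 per group (32 degrees of freedom), 80% power needs a standardised difference of 0.991. That implies SD = 15 / 0.991 = 15.1 points. The normal approximation, n = 2 × (1.960 + 0.842)² × (SD / 15)², gives 17 per group at SD 15.6. So 34 is consistent with one test at 0.05 if the SD was about 15. Nothing in it allows for several visits or arms.

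**2. Three visits, two success rules.** At correlation 0:

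- all visits must succeed: power = 0.80³ = 51.2%
- any visit may count: type I error = 1 − 0.95³ = 14.3%

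The other correlations come from simulation (at least 100,000 trials per setting, 17 per group, two-sided t tests at 0.05):

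| Assumed correlation | All visits: power | Any visit: type I error |
|---|---|---|
| 0 | 51% | 14% |
| 0.5 | 61% | 12.6% |
| 0.7 | 66% | 11.1% |
| 0.9 | 72% | 8.5% |

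The all-visits rule does not inflate type I error.

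**3. Both arms tested separately (conditional).** If the nonoperative arm had the same three visits and its own tests, there would be six tests in two independent sets. With a as the any-visit error above, the overall error is 1 − (1 − a)²: about 26%, 24%, 21% and 16% at the four correlations.

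**4. Ways to restore the stated properties, at the back-solved effect of 0.991.**

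- One named test: 5% error, 80.0% power, 34 patients.
- One test stratified by arm (31 degrees of freedom): 79.9% power.
- Bonferroni over three visits (0.05 / 3 = 0.0167): 64% power; 23 per group, 46 in total, would restore 80%.
- Each arm tested alone, if 34 is split equally (34 / 2 = 17 per arm, so 8 or 9 per group): 45.5% power with 8 per group, 50.6% with 9.
- Stratified test when BFR works in only one of two equal arms: the average effect is 0.991 / 2 = 0.496, and power is about 29%.

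**5. Timing, set side by side.** The rehabilitation text allows only passive shoulder motion in weeks 0 to 8. The visit text records strength at week 2, a visit meant for range of motion and wound healing. The endpoint is a maximum-repetition measure, but the test mode at each visit is not given. Week 6 also lies in the passive phase, although that visit may clear active motion. The 3-month visit follows the start of active exercise and comes at about the start of strengthening.

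**The case against.** The strongest reply is that this is a one-sentence gap. The contrast and test are named, and the only success wording is the hypothesis, which read literally requires every visit to succeed. That rule does not inflate type I error. This stands, and it is why the power loss, rather than the false-positive rate, is the result closest to the text. The any-visit figures need a rule that the plan neither states nor excludes. High correlation also softens both results, though at 0.9 neither returns to plan.

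Two stronger readings are tempting, and the documents support neither:

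- *Six primary tests with an error rate of up to 26%.* This needs a nonoperative visit schedule and separate testing by arm. Section 3 gives visits only in relation to surgery. Section 2 enrols patients undergoing reconstruction and section 9 takes consent before surgery, which leaves even the eligibility of nonoperative patients unclear beside sections 1 and 3.
- *A required maximum-effort test of the repaired shoulder at week 2.* This is an inference from joining the endpoint's wording to the visit list. The test mode is not stated, and the deficit is described by comparing legs, which makes that text weak evidence of what is done at week 2. What stands is that the test must be specified.

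It is also fair that 3 months is an early point, before most of the strengthening phase. A visit near week 20, or a repeated-measures analysis that keeps the aim of faster gains, could be defended. Either would still need one prespecified primary contrast.

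**Conclusion.** The concern holds. The plan makes strength primary at every visit without naming the visit, the multiplicity rule or the handling of the arms, while its sample size fits a single test. Under the rule closest to the hypothesis, power is about 51% to 72% instead of 80%. Under an any-visit rule, type I error is about 14% to 8.5% instead of 5%. These ranges rest on assumed correlations of 0 to 0.9, two-sided tests and 80% power at each visit. The 80% itself cannot be confirmed, because no SD is given.

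This is more than missing detail, because neither rule delivers both the stated alpha and the stated power. It does not show that the trial has a 26% error rate, or that it orders a maximum-effort test at week 2.

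**What to change.** **Primary analysis.** State one: BFR versus control in work deficit (involved versus uninvolved shoulder) at the 3-month visit, two-sided 0.05, stratified by operative or nonoperative arm. If only one arm is meant to be confirmatory, name that arm instead. Make other visits and per-arm estimates supportive, and change the hypothesis from every time point to 3 months.

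**Supporting text.** Say whether 34 covers one arm or both, and give the SD used. Settle whether nonoperative patients are eligible before choosing the pooled contrast; if they are, count their 3-month visit from the start of therapy.

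**Strength testing.** State that no maximum-effort dynamometer test of the operated shoulder is done at week 2, nor at any later visit until the surgeon has cleared resisted testing. Passive range of motion, pain and patient-reported outcomes can stay at every visit. Say how a patient not cleared by 3 months is handled in the primary analysis.

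**Cost.** A text amendment, with no added patients for multiplicity; stratifying costs one degree of freedom. Early strength gains become supportive or unmeasured, so faster recovery cannot be a primary conclusion. The conclusion is limited to about 3 months, before most of the week 12 to 20 strengthening. The stratified contrast falls to about 29% power if BFR works in only one of two equal arms; naming one arm avoids this but leaves the other descriptive.

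### Strength, the primary outcome, is scheduled at 2 weeks, inside the passive-only phase for operative patients (a conflict if the test is active shoulder effort), and no primary visit is named

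*Combined protocol and SAP*

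**What the plan says.** All of the following is in the combined protocol and SAP, section 3 (Study Procedures), unless noted.

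- **Arms.** Once treatment is chosen, "patients will be either in the nonoperative arm or the operative arm of this study". Randomisation to BFR or conventional therapy takes place within each arm.
- **Strength testing.** The visits are pre-operative, 2 weeks, 6 weeks and three months, and "Strength and range of motion will be recorded at each of these visits in order to assess the primary endpoint". The primary outcome line repeats that dynamometer strength is taken at every clinic visit.
- **Purpose of the early visits.** The plan describes "an early 2 week post operative visit to check range of motion and wound healing" and then "a six week visit to monitor range of motion and potentially clear for active ROM and sling discontinuation". The three-month visit comes before clearance for harder activity.
- **Rehabilitation schedule.** "Post-op weeks 0-8: Passive shoulder range of motion (ROM) only"; "Sling immobilization with active elbow, wrist and hand ROM". From week 8 the sling is dropped and the schedule lists "Being active exercises including prone row, standing internal/external rotation with bands, wall slides into shoulder flexion". Then "Weeks 12-20: Strength and function of Side lying shoulder external rotation, increase resistance band exercises". The heading over these lines covers surgical and non-surgical patients alike, although the first line is worded as post-operative.
- **Endpoint and analysis.** The endpoint is a 15% deficit in dynamometer total work over maximal repetitions. Joint, movement and contraction mode are not given, and the limb compared is called a leg. The sample size is 34 (17 per group) for 80% power at alpha 0.05. Continuous data are compared by two-group t tests. No visit is singled out, and there is no repeated-measures model or multiplicity rule.
- **Hypothesis (section 1).** Greater strength gains with BFR are expected at every time point.

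**The concern.** Two separate matters are at stake.

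**Schedule.** The visit paragraph asks for a strength measurement two weeks after repair. At that time the rehabilitation schedule allows no active shoulder motion at all. If the test is active shoulder effort, the assessor must either load a fresh repair in a way the schedule does not allow, or leave the primary outcome missing at that visit. No text exempts the visit or names a substitute test.

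**Primary visit.** Whatever the test is, the plan does not say which follow-up visit answers the primary question. The primary analysis is therefore not uniquely defined, and neither the 5% error rate nor the 80% power can be attached to it.

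**Working it through.** **1. Timing of visits against the rehabilitation schedule (operative patients)**

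Three months is 84/7 = 12 to 91/7 = 13 weeks.

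| Visit | Phase in the schedule | Active shoulder test compatible? |
|---|---|---|
| Week 2 | 0-8, passive only, sling | No |
| Week 6 | 0-8, but the visit may clear active motion | Ambiguous |
| Week 12-13 | start of 12-20 | Probably; to be confirmed |

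- *Week 6.* The visit paragraph may clear active motion and sling removal then, while the schedule places both from week 8. As there is no week-8 visit, week 6 may simply be where the week-8 change is decided. In either case, clearance for active motion is not clearance for resisted effort.
- *Three months.* Band exercises began 12 - 8 = 4 to 13 - 8 = 5 weeks before. The strength phase began 12 - 12 = 0 to 13 - 12 = 1 week before.

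Follow-up tests inside the passive phase, out of 3 per operative patient:
- active shoulder test, with week-6 clearance immediate and covering resisted effort: 1/3 = 33%
- active shoulder test otherwise: 2/3 = 67%
- test of the elbow, wrist or hand, which the schedule leaves active: 0/3

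**2. The plan's own sample size**

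The SD is not given, so 17 per group cannot be reproduced from stated inputs. Solving backwards for a two-sided t test (sidedness assumed) at alpha 0.05, 17 per group and 80% power gives a standardised difference d = 0.991, so SD = 15/0.991 = 15.1 points. The stated size is consistent with one comparison at one visit.

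**3. Consequences of naming no visit**

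Inputs: 17 per group, 3 follow-up visits, and a two-sided t test at 0.05 at each. Two inputs are assumed: between-visit correlations of 0, 0.5 and 0.9, and an equal effect of d = 0.991 at every visit. The results come from simulation with 400,000 runs per correlation.

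| Correlation | False positive, any visit counts | False positive, all must be significant | Power, all must be significant |
|---|---|---|---|
| 0 | 14.3% | 0.01% | 51% |
| 0.5 | 12.6% | 0.3% | 61% |
| 0.9 | 8.5% | 2.2% | 72% |

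Checks at correlation 0: 1 - 0.95^3 = 0.1426; 0.05 x 0.025^2 x 4 = 0.05^3 = 0.000125; 0.80^3 = 0.512.

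With one named visit, the figures are 5% and 80%.

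**4. Keeping three primary visits instead**

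With Bonferroni, alpha is 0.05/3 = 0.0167 per visit. Power at each visit with 17 per group falls to 64%. Restoring 80% needs 23 per group, or 46 in place of 34.

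**The case against.** The strongest reply is that no hazard has been shown. The plan never states the joint or mode of the test. The phrase about maximal repetitions stands in the same paragraph that compares legs, so it is weak evidence about a shoulder test. The passive-only lines are a therapy schedule and do not mention testing. Section 12 also provides for clinic visits that monitor therapy progress and adherence. This stands to the extent that the conflict must be stated as conditional. A reader might infer that the protocol orders maximal loading of a two-week-old repair, and the documents do not establish that. Still, active shoulder effort is the likely reading. The trial concerns rotator cuff strength, the pre-operative exercises are shoulder movements, and passive motion by an examiner does not measure strength. Nothing in the text resolves the point the other way.

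A reader might also infer that the passive-only rule plainly spares non-operative patients. The post-operative wording suggests so, but the heading covers both groups, so the question is open.

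On the statistics, the plan states no rule under which any visit may win. The hypothesis points to every visit, and under that rule the false positive rate is below 5%. This stands: error inflation and power loss are alternatives, and it would be wrong to charge the plan with both. If the early tests were skipped in operative patients, the three-visit figures would not apply to them either. What remains is that the plan does not choose a rule.

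Finally, no bias between BFR and control follows, because both cohorts share one schedule.

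**Conclusion.** The point holds in conditional form for the schedule and without condition for the missing primary visit.

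- **Schedule.** If the test is active shoulder effort, the 2-week strength test in operative patients contradicts the rehabilitation rule, and the 6-week test may do so. That is 1 or 2 of 3 follow-up tests per operative patient. If the test is of a joint left active, it is none.
- **Non-operative patients.** Whether the passive-only lines apply to them needs to be settled.
- **Primary visit.** None is named. Depending on the rule later adopted, either the false positive rate is about 9% to 14%, or power is about 51% to 72%. Both ranges rest on the assumed correlations, and the second also on an equal effect at each visit.

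This does not show that 34 is the wrong sample size, nor that the study's aims must be abandoned. It is a cheap improvement: a safer schedule and a defined primary analysis for a change of wording.

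**What to change.** In section 3, replace the sentence on recording strength at every visit with, for example:

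> Operative patients: shoulder dynamometer strength is measured pre-operatively and at three months. It is not measured at 2 weeks. It is measured at 6 weeks only if the surgeon explicitly clears resisted testing, and those values are descriptive. Range of motion within permitted limits, pain and patient reported outcomes are recorded at every visit. The three-month visit is the single primary time point for the strength comparison; earlier strength values are secondary.

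Then:
1. Change the primary outcome line to match.
2. State the joint, movement, contraction mode and effort of the test, and correct the limb named. Have the clinical team confirm that the test is allowed at three months.
3. State whether week-6 clearance takes effect at week 6 or week 8.
4. State whether the passive-only and sling lines apply to non-operative patients.
5. In section 1, make the three-month comparison the primary one. The aims need no further rewriting.

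**Cost.** The sample size stays at 34. Each operative patient loses one or two of three follow-up strength values, so k operative patients lose k to 2k tests. The plan does not give k, nor say whether 34 is the whole trial or one arm. Early speed of strength gain is described less well in that arm, and its follow-up strength rests largely on one visit. As an illustration, if missed three-month visits leave 15 or 14 per group, power falls from 80% to 75% or 71% at d = 0.991. If the test is not allowed at three months, a later strength visit is needed, which is more than a wording change.

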11. PRIVACY AND CONFIDENTIALITY

Data will be stored on a password protected HFH computer. Patient data will either be located in the chart or kept in a locked spreadsheet that contains no patient identification aside from a unique patient ID associated with their MRN. This will only be accessible to the investigators. Data will be destroyed following publication or after six months of inactivity. We will also obtain HIPAA authorization in order to access the medical record.

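### Enrolment and data collection share one June 2020 to May 2021 window with no close-out rule, so late enrolees may lack the three-month strength value

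*Combined protocol and SAP*

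**What the plan says.** All of the timing is in section 3 (Study Procedures) of the combined protocol and SAP.

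- **Calendar.** Recruitment opens in June 2020 ("Plan to recruit patients starting in June 2020"). One window then covers both enrolment and measurement, and the next step follows at once: "Will enroll patients and collect data from June-2020 to May 2021. Manuscript writing and submission to occur in June 2021". No section gives an earlier close of enrolment, a follow-up period after May 2021, or a rule tying the end of data collection to the last patient's last visit.
- **Time before surgery.** "Patients undergoing operative rotator cuff repair (RCR) will undergo preoperative rehabilitation prior to surgery for two weeks". This home programme is done with or without the cuff according to random allocation, so it comes after consent and randomisation.
- **Visits.** There is a preoperative visit, then visits at two weeks, at six weeks, and "a three month visit prior to clearance to being return to more aggressive activity". No later visit is listed.
- **Primary outcome.** Dynamometer strength is measured at every visit: "Strength and range of motion will be recorded at each of these visits in order to assess the primary endpoint". No single visit is named as the primary time point.
- **Rehabilitation phases.** Weeks 0 to 8 are passive shoulder motion only, weeks 8 to 12 are active motion, and weeks 12 to 20 are strengthening.

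**The concern.** A patient's follow-up takes about a quarter of a year, but the plan ends enrolment and measurement in the same month and starts writing in the next. Unless accrual stops well before May 2021, the calendar will cut off follow-up for the last patients in.

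The visit lost first is the three-month one, and it matters most for the study's question. The two-week and six-week visits both fall in the passive phase. Three months is the only scheduled postoperative visit after active exercise has begun. The study hypothesis in section 1 concerns strength gains at all time points, so this visit is part of the planned answer.

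The plan also has nothing to absorb the loss. The sample size of 34 carries no stated allowance for dropout, and the analysis paragraph (two-group t tests, with nonparametric alternatives) has no method for missing values. Patients without the three-month value would simply drop out of that comparison, after taking on the rehabilitation and, in one group, the cuff.

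**Working it through.** **Inputs from section 3:** window June 2020 to May 2021; 2 weeks of preoperative rehabilitation; last visit at three months; N = 34 (17 per group).

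**Assumptions:** the window runs from 1 June 2020 to 31 May 2021, which is 52 weeks; three months means 12 or 13 weeks; surgery follows the two weeks without delay; nonoperative patients are counted from enrolment, because the plan does not say where their clock starts.

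**The plan's own figure.** The 34 cannot be reproduced, because no standard deviation is given for the 15% difference. The point does not depend on it; 34 serves below only as a count of patients.

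**Step 1. Weeks from enrolment to the three-month visit.**
- Operative: 2 + 12 = 14, or 2 + 13 = 15.
- Nonoperative: 12 or 13.

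**Step 2. Latest enrolment date with a three-month visit inside the window** (31 May 2021 minus the weeks in step 1).

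| Weeks needed | Arm | Latest enrolment | Share of window after that date |
|---|---|---|---|
| 12 | Nonoperative | 8 March 2021 | 12/52 = 23% |
| 13 | Nonoperative | 1 March 2021 | 13/52 = 25% |
| 14 | Operative | 22 February 2021 | 14/52 = 27% |
| 15 | Operative | 15 February 2021 | 15/52 = 29% |

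If visits could continue to 30 June 2021, the operative dates would move only to 24 March (14 weeks) and 17 March (15 weeks).

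**Step 3. Illustrative number of patients, assuming even accrual of 34 over the 52 weeks** (34 × weeks/52).
- 12 weeks: 34 × 12/52 = 7.8
- 13 weeks: 34 × 13/52 = 8.5
- 14 weeks: 34 × 14/52 = 9.2
- 15 weeks: 34 × 15/52 = 9.8

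If all 34 are operative and need 14 weeks, about 9 lack the three-month value and about 25 have it. Any mix of the two arms falls between 7.8 and 9.8, before any surgical waiting time. If accrual ends by mid-February 2021, the number is zero.

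**Step 4. What late operative enrolees can still give.** The six-week visit falls 2 + 6 = 8 weeks after enrolment and the two-week visit 2 + 2 = 4 weeks after.
- Enrolled at least 8 but fewer than 14 weeks before the close: baseline, two-week and six-week strength.
- At least 4 but fewer than 8 weeks: baseline and two-week strength.
- Fewer than 4 weeks: baseline only.

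**The case against.** The best defence is that the timeline is a month-level plan. It does not say that enrolment stays open until 31 May 2021 or that visits stop on that day. It can be read as an overall study window, with accrual ending early enough for the last visits, and then nobody is affected. This stands as far as it goes: the loss is conditional. But nothing in the protocol requires accrual to end early, and read plainly the sentence permits the cut-off.

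Several stronger readings are tempting, and the documents do not support them.

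- **That the primary endpoint itself is lost, so late patients contribute nothing.** Three months is not named as the primary time point. Strength counts at every visit, and step 4 shows that many late enrolees would still give postoperative values.
- **That the missing values could never be added, because the data are destroyed.** Section 11 says "Data will be destroyed following publication or after six months of inactivity". The triggers are publication or inactivity, not the June 2021 submission, and patients still in follow-up are not inactive.
- **That patients who cannot finish the 20-week programme in the window are also lost.** No assessment is scheduled after three months, so no planned outcome is missed there.
- **That power falls by a known amount.** Using the standardised difference that 17 per group can detect with 80% power in a two-sided t test (0.99), 12 to 13 per group would have about 64% to 68%. That figure rests on even accrual, a back-solved standard deviation and a three-month comparison that the plan does not single out. It is not an estimate for this trial.

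**Conclusion.** The concern holds in conditional form. The plan gives one window for enrolment and data collection, and neither a last-enrolment date nor a close-out rule. If enrolment uses the full window, operative patients enrolled after about mid-February 2021, and nonoperative patients enrolled after about early March 2021, would miss the last scheduled strength measurement.

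The dates rest on a 31 May 2021 close and on three months meaning 12 to 13 weeks. The size (about 9 of 34, or 27%; 23% to 29% across 12 to 15 weeks) rests also on even accrual, which the documents do not state. It is an illustration, not a forecast. Surgical waiting time beyond two weeks would make the cut-off earlier; accrual that ends by mid-February would remove the problem. Because the plan has no safeguard and the repair is a single sentence, the change should be made.

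**What to change.** In section 3, replace the sentence that sets the shared window with:

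> Data collection continues until the last randomised patient completes the final scheduled (three-month) strength visit; analysis and manuscript writing begin only after that visit.

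This rule is safer than a fixed enrolment cut-off. For example, a patient enrolled on 22 February 2021 would have surgery on 8 March at the earliest, and three calendar months later is 8 June, outside the window. That date works only if three months means exactly 12 weeks and surgery is not delayed.

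The cost is a later manuscript. If enrolment runs to 31 May 2021, the last operative three-month visit falls 14 to 15 weeks later, about 6 to 13 September 2021, and later still if patients wait for surgery. If accrual finishes early, there is little or no delay.
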